9.4.2 ANALYSIS OF THE PRIMARY EFFICACY ENDPOINT(S)

The primary efficacy variables (see Section 8.1) will be analyzed at month 3 using an analysis of covariance [ANCOVA] model with baseline MGS score and duration of disease as covariates and treatment (AZR-MD-001 ointment/semi-solid drug or vehicle/placebo) as factors in the model. Pairwise comparisons will be performed for each AZR-MD-001 ointment/semi-solid drug treatment group versus vehicle/placebo using t-tests of the least square means from this model. Two-sided confidence intervals (95%) will be provided for the differences between treatments. To support regions (e.g. EU) requiring 6 months of efficacy data in the Expansion Cohort, the same model will be applied at 6 months.

Details of other efficacy analyses will be provided in the statistical analysis plan.

9.4.3 ANALYSIS OF THE SECONDARY ENDPOINT(S)

The secondary efficacy variables (see Section 8.1) will be analyzed using an analysis of covariance [ANCOVA] model with baseline MGS score and duration of disease as covariates and treatment (AZR-MD-001 ointment/semi-solid drug or vehicle/placebo) as factors in the model. Pairwise comparisons will be performed for each AZR-MD-001 ointment/semi-solid drug treatment group versus vehicle/placebo using t-tests of the least square means from this model. Two-sided confidence intervals (95%) will be provided for the differences between treatments. To support

regions (e.g. EU) requiring 6 months of efficacy data in the Expansion Cohort, the same model will be applied at 6 months.

Descriptive statistics (change from baseline variables) will be tabulated for the following within treatment group changes in the mITT population:

- Cohort 1: Patients in the AZR-MD-001 ointment/semi-solid drug treatment group: changes from baseline to days 14, month 1, month 1.5 and month 3
- Patients in the AZR-MD-001 vehicle group: changes from baseline to days 14, month 1, month 1.5 and month 3

Expansion Cohort:

- Patients in the AZR-MD-001 ointment/semi-solid drug treatment group: changes from baseline to days 14, month 1.5, month 3, month 4.5 and month 6
- Patients in the AZR-MD-001 placebo group: changes from baseline to days 14, month 1.5, month 3, month 4.5 and month 6

Within each treatment group, shift tables for complete treatment response (yes/no) in the study eye will be presented for patients in the mITT population for endpoint signifying a “clinical cure” (Proportion of patients with a MGS score > 12 ; Proportion of patients with a change from baseline in MGYLS score of ≥ 5 ; Proportion of patients with a MGYLOS score of > 2 ; Proportion of patients with a TBUT > 10 seconds at each visit; Proportion of patients with a Schirmer’s test ≥ 10 mm at each visit; Proportion of patients with a Total OSDI < 13 at each visit; and Proportion of patients with a SPEED Score < 6 ; Proportion of patients with an Average VAS or Worst VAS score decreased by ≥ 5 at each visit.

Cohort 1:

- Patients in the AZR-MD-001 ointment/semi-solid drug treatment group: changes from baseline to days 14, month 1, month 1.5 and month 3.
- Patients in the AZR-MD-001 vehicle group: changes from baseline to days 14, month 1, month 1.5 and month 3.

Expansion Cohort:

- Patients in the AZR-MD-001 ointment/semi-solid drug treatment group: changes from baseline to days 14, month 1.5, month 3, month 4.5 and month 6
- Patients in the AZR-MD-001 placebo group: changes from baseline to days 14, month 1.5, month 3, month 4.5 and month 6

The Logistic Regression method for general association, stratified by baseline MGS score and duration of disease will be used to compare treatments with respect to the proportion of patients achieving a “clinical cure” in the study eye. Odds ratio along with 95% CI will be obtained by pairwise comparisons will be performed for each AZR-MD-001 treatment groups versus vehicle.

9.4.4 SAFETY ANALYSES

Safety measures will be analyzed using the safety population. Medical Dictionary for Regulatory Activities (MedDRA) nomenclature will be used to code adverse events. Treatment-emergent adverse events will be summarized. The adverse events will be classified into ocular and nonocular types and will be summarized separately. Detailed methods for the analyses of adverse events and other safety variables will be described in the analysis plan.

9.4.5 BASELINE DESCRIPTIVE STATISTICS

In general, continuous data will be summarized with descriptive statistics (number of patients, mean, standard deviation, median, minimum, and maximum) and will be analyzed using analysis of variance (ANOVA) techniques or 2-sample t-tests for between-group comparisons, and paired t-tests for within-group analyses. Categorical variables will be summarized by sample size (N), frequency count, and percent, and they will be analyzed using Pearson’s chi-square test or Fisher’s exact test (if the expected cell count is less than 5 in 25% or more of the cells). Ordinal variables will be analyzed using the Cochran-Mantel-Haenszel (CMH) or the Wilcoxon rank-sum test for between-treatment comparisons and the sign-rank test for within-treatment comparisons.

9.4.6 PLANNED INTERIM ANALYSES

Two official interim analyses are planned for Cohort 1 of the study. The first interim analysis is planned for after the 10th patient in Cohort 1, Group 3 exits the study. Only data collected up to the last patient exiting the study from Cohort 1, Group 3 will be included in the first interim analysis. All ongoing patients in Cohort 1 will remain masked until the second interim analysis.

A second interim analysis is planned after the final patient from Cohort 1 exits the study (Cohort 1, Group 4). Outcomes from this analysis will assist in the confirmation of the study drug concentration and frequency to be used for the Expansion Cohort.

One interim analyses is planned for the Expansion Cohort of the study. The interim analysis is planned for after the last enrolled patient completes the month 3 visit. Only data collected up to the month 3 visit will be included in the interim analysis. The primary endpoints for the US will serve as an Interim Analyses for the Month 6 primary endpoints. The sample size may be adjusted for power or to address any concerns for alpha inflation.

A final database lock will occur at the completion of the Expansion Cohort and the safety, tolerability, and efficacy data from Cohort 1 and the Expansion Cohort will be analyzed separately and in a combined fashion. At the final analysis, statistical significance will be declared for 2-sided p-values ≤ 0.05 .

Given the exploratory nature of Cohort 1 no adjustments for multiplicity will be applied across the primary or secondary endpoints in this cohort. Multiplicity will be controlled across the primary endpoints in the Expansion Cohort as described in Section 9.4.1.

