Interim Analysis: An interim analysis (Primary Endpoint for the U.S.) is planned after the final enrolled patient completes the month 3 visit. Only an independent biostatistician will be unblinded to the treatment patients actually received and only summary efficacy and safety tables will be provided. Outcomes from this analysis will assist in the confirmation of the study power calculations and potentially as part of a rolling submission to global regulatory agencies.

Figure 1 Study Flow – Multicenter, double-masked, vehicle-controlled, randomized, parallel group study carried out in 2 sequentially overlapping cohorts

a: Cohort 1:

b: Expansion Cohort:

The primary endpoints for the US will serve as an Interim Analyses for the Month 6 primary endpoints. The sample size may be adjusted for power or to address any concerns for alpha inflation.

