9.1.2 EXPANSION COHORT

Estimates for sample size calculations are from the final Cohort 1 interim analysis from Azura Clinical Protocol AZ201801. The mean response of 0.77 and a standard deviation for MGYLS of 2.28 units was observed for control and a mean response of 2.77 units and a standard deviation for MGYLS of 3.35 units was observed for AZR-MD-001 0.5%. A sample size of 45 subjects per group will have 90% power to detect a difference of 2.0 units between the active treatment group and the placebo group using a two-sample t-test at a significance level of 0.05. The standard deviation for Total OSDI was 6.31 units for control and 8.34 units for the high dose. A sample size of 58 subjects per group will have 90% power to detect a difference of 4.52 units between the active treatment group and the control group using a two-sample t-test at a significance level of 0.05. To allow for additional site to site variability the sample size per group will be increased to approximately 75 patients.

Multiplicity Consideration: To address the multiple primary endpoints defined in this study, the primary endpoints have been prioritized into a hierarchical structure. For example, in order to test the primary symptom endpoint of Total OSDI, the primary sign endpoint of MGYLS must be statistically significantly higher in the AZR-MD-001 treatment group compared to the vehicle treatment group using a two-sided significance level of 0.05 for a given concentration. The final order of the endpoints will be defined in the Statistical Analysis Plan (SAP) prior to unmasking the study. Using this strategy, the family-wise Type I error rate will be maintained at the 0.05 significance level for the two primary endpoints.

Interim Analysis (Primary efficacy endpoint for the US): An interim analysis is planned after the final enrolled patient completes the month 3 visit. Only an independent biostatistician will be unblinded to the treatment patients actually received and only summary efficacy and safety tables will be provided. Outcomes from this analysis will assist in the confirmation of the study power calculations and potentially as part of a rolling submission to global regulatory agencies.

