2.3.2. Sample Size Re-Estimation

As described in [Section 1.2](#), additional patients may be enrolled if the observed variability within the Expansion Cohort is higher than anticipated, after the evaluation of the MGYLS and OSDI total score changes from baseline to Month 3 using LOCF imputation. The standard deviation of the pooled treatment groups will be calculated in a masked fashion for both MGYLS and OSDI total score and compared to the pooled standard deviations of 3.63 (MGYLS) and 8.71 (OSDI) from the integrated study. No unmasking will be performed as part of this re-estimation.

The power calculations from the integrated studies will be re-derived based on pooled standard deviations (resulting in 0.918 for the MGYLS comparison of AZR-MD-001 0.5% to placebo, and >0.999 for the other comparisons), for the sole purpose of providing a basis for comparison to the power re-calculations based on the pooled standard deviations from the Expansion Cohort.

Patients may be added up to the specified numbers, to maintain the current power of the study, if possible. For example:

- If the pooled standard deviation is 3.64-3.85 for MGYLS or 8.72-9.64 for OSDI total score, up to 30 additional patients may be randomized (10 per treatment arm).
- If the pooled standard deviation is 3.86-4.07 for MGYLS or 9.65-10.20 for OSDI total score, up to 60 additional patients may be randomized (20 per treatment arm).
- If the pooled standard deviation is 4.08-4.29 for MGYLS or 10.21-10.74 for OSDI total score, up to 90 additional patients may be randomized (30 per treatment arm).

The specific sample sizes needed will be recalculated using the initial mean changes from baseline from the integrated studies, in conjunction with the pooled standard deviations from the Expansion Cohort, using the following pseudocode:

```
proc power;
  twosamplemeans test=diff dist=normal groupmeans=(2.77 0.77)
  stddev=xxx sides=2 power=.918 npergroup=.;
run;
proc power;
  twosamplemeans test=diff dist=normal groupmeans=(3.79 0.77)
  stddev=xxx sides=2 power=.999 npergroup=.;
run;
proc power;
  twosamplemeans test=diff dist=normal groupmeans=(-8.36 -0.81)
  stddev=xxx sides=2 power=.999 npergroup=.;
run;
proc power;
  twosamplemeans test=diff dist=normal groupmeans=(-5.33 -0.81)
  stddev=xxx sides=2 power=.999 npergroup=.;
run;
```

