11. INTERIM ANALYSES

No official interim analysis will be performed.

As described in [Section 1.2](#) and [Section 2.3.2](#), a sample size re-estimation will be performed, in a masked fashion, after all patients complete Month 3. These analyses will be limited to calculation of pooled standard deviations for MGYLS and OSDI total score, and the sample size re-estimation using pseudocode presented in [Section 2.3.2](#). No data summaries or comparisons between treatment groups will be created, and no unmasking will occur.

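### The protocol lets the sample size change after an unmasked Month 3 comparison, with no rule and no adjusted test, so the 0.05 level of the Month 6 regional test is not secured

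*Protocol*

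**What the plan says.** **Protocol.** For the Expansion Cohort, change from baseline in MGYLS and in Total OSDI is primary at Month 3 for the US and at Month 6 for regions that want longer follow-up, such as the EU (Sections 1.2, 8.1.4 and 9.4.1). On timing, Section 9.4.6 says "The interim analysis is planned for after the last enrolled patient completes the month 3 visit". On masking, Section 9.1.2 says "Only an independent biostatistician will be unblinded to the treatment patients actually received and only summary efficacy and safety tables will be provided". On use, the same section says "Outcomes from this analysis will assist in the confirmation of the study power calculations". The note to Figure 1 in Section 1.2 states "The primary endpoints for the US will serve as an Interim Analyses for the Month 6 primary endpoints", and both that note and Section 9.4.6 continue: "The sample size may be adjusted for power or to address any concerns for alpha inflation". Section 9.4.6 closes the matter with "At the final analysis, statistical significance will be declared for 2-sided p-values" of 0.05 or less. For multiplicity it refers to Section 9.4.1, which orders sign before symptom within a concentration and does not mention the Month 3 look or a changed sample size.

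**SAP.** Section 11 states "No official interim analysis will be performed". Sections 1.2 and 2.3.2 provide a different step: a pooled-SD review of MGYLS and OSDI before the Month 3 freeze, of which Section 2.3.2 says "No unmasking will be performed as part of this re-estimation". If patients are added, freeze and unmasking wait until they have reached Month 3. Sections 8 and 8.3.2 make Month 4.5 and Month 6 p-values descriptive. Section 1 limits this SAP to authorities that accept Month 3. Section 12, the list of departures from the protocol, mentions neither the dropped interim analysis, nor the masked rule, nor the changed status of Month 6.

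**The concern.** Alpha is controlled by the critical value, by how alpha is split, or by how the stages are combined. It is not controlled by enrolling more patients. If the number added depends on the observed Month 3 arm difference, and Month 3 and Month 6 results in the same patients are correlated, the ordinary Month 6 statistic no longer has its nominal null distribution. The protocol permits that sequence, names alpha inflation as a reason for it, and keeps 0.05.

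At stake is the confirmatory Month 6 claim outside the US. Because the SAP covers only Month 3 authorities, the protocol clause is the only text among the documents supplied that governs a confirmatory Month 6 test. The two documents also give the sponsor two incompatible procedures for changing the sample size at the same calendar point.

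**Working it through.** **1. The plan's own figures (Protocol 9.1.2; SAP 2.3.2).** With n = 2(SD/Δ)²(z0.975 + z0.90)² and (1.960 + 1.282)² = 10.507:

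- MGYLS: SD = √[(2.28² + 3.35²)/2] = 2.865 and Δ = 2.0, giving n = 43.1. The t-test solution is 44.1, rounded up to 45. The protocol says 45.
- OSDI: SD = √[(6.31² + 8.34²)/2] = 7.395 and Δ = 4.52, giving n = 56.3. The t-test solution is 57.2, rounded up to 58. The protocol says 58.
- SAP reference power for MGYLS, 0.5% against placebo, at 75 per arm and SD 3.63: t-test 0.918, as stated.

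The base design reproduces, so 75 per arm is a sound starting point.

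**2. Month 6 error after an unmasked change.** Take one dose against placebo on one endpoint, under the null, with normal data, no dropout and 75 per arm at the look. Let z3 be the Month 3 statistic, ρ its correlation with the Month 6 statistic, m the number added per arm, and f = 75/(75 + m). Given z3, the ordinary Month 6 statistic is normal with mean ρ·z3·√f and variance 1 − ρ²f. Type I error is the probability that its absolute value reaches 1.96, averaged over z3 ~ N(0,1) under the rule that chooses m.

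The mechanism shows at ρ = 0.7. When z3 = 2.5 and m = 0, the mean is 1.75 and the SD 0.714, so the rejection probability is 0.384. With m = 75 the mean is 1.237 and the SD 0.869, and it falls to 0.203. When z3 = 0 it rises from 0.006 (m = 0) to 0.024 (m = 75). Adding patients after a weak Month 3 result and none after a strong one therefore raises the average. The opposite pattern lowers it.

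The documents do not give ρ, so it is shown over an assumed range. The cap of 30 per arm is borrowed from the largest example tier in SAP 2.3.2. The cap of 75 (doubling) is an assumption.

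| Rule for m | ρ = 0.5 | ρ = 0.7 | ρ = 0.85 |
|---|---|---|---|
| No change | 0.050 | 0.050 | 0.050 |
| Worst choice for every z3, up to 30 | 0.054 | 0.057 | 0.060 |
| Worst choice for every z3, up to 75 | 0.057 | 0.062 | 0.067 |
| Add 75 whenever Month 3 is not significant | 0.053 | 0.057 | 0.063 |
| Add 75 only if absolute z3 is between 1.40 and 1.96 | 0.048 | 0.046 | 0.046 |

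At ρ = 0 every rule gives 0.050.

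**3. The alternatives.** The SAP's masked rule (MGYLS tiers, 40,000 simulated null trials) gives 0.050. A combination of the two stages with weights fixed in advance (simulated at ρ = 0.7, weights 75/105 and 30/105) also gives 0.050.

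**4. A separate condition.** With no change of sample size, if success at Month 3 or at Month 6, each at 0.05, counted as one overall claim, the error would be 0.091, 0.084 and 0.075 for the same three correlations.

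**The case against.** A reader might infer that the clause inflates the error rate and that the Month 6 claim cannot have a 0.05 level. The documents do not support that. No rule is written, so the effect is undetermined, and the last row of the table shows a recognisable rule that stays below 0.05. The larger figures are maxima over every possible choice, under caps and a correlation that the documents do not supply. An adjustment for power could also rest on variability alone. All of this stands, so the defensible statement is that error control is missing.

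The wording can also be read charitably: if a regulator asked for a smaller alpha, a larger sample would recover power. At 0.025 the normal-approximation sizes go from 44 to 51 (MGYLS) and from 57 to 67 (OSDI). The rationale in the amendment's summary of changes, which mentions regulators' requests, fits this reading. But no lower alpha appears anywhere and Section 9.4.6 keeps 0.05, so it does not close the gap.

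A reader might also infer that the SAP's Month 3 test is compromised. It is not: the masked review comes before unmasking. Because the same patients supply both time points, following the SAP would in practice settle the sample size for Month 6 as well. That makes the repair largely one of protocol wording. It does not remove the clause for regions outside the SAP's scope.

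Two limits remain. SAP Section 1 refers to country-specific addenda, and a separate Month 6 plan may exist, so the conclusion concerns only the documents supplied. Section 12 presents its list as partial, and the SAP states its masked rule openly, so the omission is a matter of traceability rather than concealment.

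**Conclusion.** The concern holds as a failure to secure the error rate. The protocol permits a sample-size change after an unmasked Month 3 comparison, gives no rule, cap or alpha-preserving test, and keeps two-sided 0.05 for the Month 6 regional primary test. Per comparison, the resulting error runs from slightly below 0.05 to a worst case of 0.060 with up to 30 added per arm or 0.067 with up to 75, on the assumptions in the working. The size is modest, but a confirmatory claim depends on it and the correction is cheap, so it should be made. The Month 3 primary analysis under the SAP stands. The two documents still disagree on whether there is an interim analysis, on how the sample size may change, and on whether Month 6 is primary or descriptive.

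**What to change.** 1. Delete the sample-size sentence from Protocol 9.4.6 and from the Figure 1 note.
2. State in the protocol that the masked pooled-SD review in SAP 2.3.2, completed before any Month 3 unmasking, is the only permitted sample-size change, and that no patients are added afterwards.
3. List in SAP Section 12 the dropped interim analysis, the masked rule and the changed status of Month 6.
4. State that Month 3 and Month 6 support separate regional claims. Testing Month 6 at 0.05 without adjustment is sound only on that condition.
5. Reconcile Month 6 as a primary endpoint in the protocol with Month 6 as descriptive in the SAP. If it stays confirmatory for any region, name the plan that governs that test.

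The cost is a wording amendment and the loss of the option to enlarge the trial after unmasking. If the sponsor wants to keep that option, the adaptation rule and an alpha-preserving test, such as a combination test with fixed weights, must be specified before unmasking.

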9.4.7 SUB-GROUP ANALYSES

Patients will be stratified by duration of MGD diagnosis (i.e., < 5 years or ≥ 5 years) and baseline MGS score for the qualified eye (i.e., the eye meeting the inclusion/exclusion criteria). If the eyes have the same MGS score the right eye will be selected as the study eye.

Thus, subgroup analyses are planned for the 4 groups defined by the 2 stratification factors:

1. MGD diagnosis < 5 years and MGS score for the qualified eye < 6
2. MGD diagnosis < 5 years and MGS score for the qualified eye ≥ 6 and ≤ 12
3. MGD diagnosis ≥ 5 years and MGS score for the qualified eye < 6
4. MGD diagnosis ≥ 5 years and MGS score for the qualified eye ≥ 6 and ≤ 12 .

9.4.8 TABULATION OF INDIVIDUAL PARTICIPANT DATA

Individual participant data will be listed by measure and time point.

9.4.9 EXPLORATORY ANALYSES

The statistical analysis plan (SAP) will provide a detailed description of the planned exploratory statistical analysis.

10 REGULATORY, ETHICAL, AND STUDY OVERSIGHT CONSIDERATIONS

10.1 INDEPENDENT ETHICS COMMITTEE

Before initiation of the study at each study center, the protocol, the ICF, other written material given to the participants, and any other relevant study documentation will be submitted to the appropriate IEC/IRB. Written approval of the study and all relevant study information must be obtained before the study center can be initiated or the study drug is released to the investigator. Any necessary extensions or renewals of IEC/IRB approval must be obtained for changes to the study such as amendments to the protocol, the ICF or other study documentation. The written approval of the IEC/IRB together with the approved ICF must be filed in the study files. The investigator will report promptly to the IEC/IRB any new information that may adversely affect the safety of the patients or the conduct of the study. The investigator will submit written summaries of the study status to the IEC/IRB as required. On completion of the study, the IEC will be notified that the study has ended.

